**The Effect of Etelcalcetide on Bone-tissue Properties and Calcification
Propensity in End Stage Kidney Disease**

Principal Investigator: [name], MS

AAAR6244

NCT03960437

Protocol Version January 3, 2020

Title: The effect of etelcalcetide on bone-tissue properties and calcification propensity in end stage kidney disease

Hypotheses: Our hypothesis is that etelcalcetide treatment improves bone tissue-properties and bone mineral density by reducing remodeling. We also hypothesize that etelcalcetide's ability to lower serum calcium will decrease propensity of serum to calcify as determined by T50.

[figure not shown]
Background and Study Objectives

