Bone-tissue properties. We will use an integrated Raman/Nanoindentation system, which permits precise measurement of localized bone tissue properties (e.g., mineral/matrix, collagen) and indentation properties (e.g., hardness) within identical regions. Areas within the TCN and demeclocycline double label will be assessed for nanoindentation properties, and subsequently the same spatial location will be assessed for Raman-based measurements. Nanoindentation will occur using a Berkovich diamond indenter loading to a peak load of 10mN, a strain rate of 0.05 seconds and a holding period of 10 seconds. Oliver and Pharr methods will be used to determine the stiffness and hardness of the unloading curves. A total of 12-15 indentations will be performed within a given region. Following indentation, the same spatial regions will be assessed with Raman spectroscopy to determine the phosphate and matrix peaks after background and baseline shift correction. The ratio of phosphate:mineral will be calculated, along with other parameters (crystallinity and collagen crosslinking).

Hypothesis 2. Etelcalcetide will improve bone density, microarchitecture, and biomechanical competence in patients with ESKD.

Aim 2. To test if 6-months of treatment with etelcalcetide improves femoral neck areal BMD measured by DXA and failure load at the ultradistal radius measured by application of finite element analysis to HR-pQCT datasets. We will also quantify the effect of 6-months treatment with etelcalcetide on changes in areal BMD at the spine, total hip, and one-third and ultradistal radius measured by DXA, and cortical and trabecular volumetric BMD and microarchitecture, cortical porosity and tissue mineral density, and biomechanical competence at the ultradistal radius and tibia measured by HR-pQCT with application of finite element analysis.

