Statistical methods (for analysis of primary and secondary endpoints or primary/interim analysis)

For All Aims, distributions will be examined and Anderson-Darling tests of normality and Q-Q plots will be used to guide the application of transformations to normalize the values prior to inferential testing. (Data analyzed from transformations will be reported in raw units). Inferential tests will be adjusted for multiple comparisons within a measurement domain (BMD within DXA, cortical, trabecular and FEA within HRpQCT, and each of the four compartments within histomorphometry) using a resampling, step-down procedure to control the family-wise error rate. We favor this over a false-discovery rate approach given the limited number of hypotheses within each measurement domain and that the measurement domains are traditionally seen as free to vary independently of each other^{11, 12}.

For Aim 1. A two-tailed dependent T-test of the change in hardness measured by Ramen nano-indentation and mineralization measured by histomorphometry obtained primary dynamic and secondary structural bone quality

outcome values from the pre-treatment baseline to the 6-month endpoint will be reported with an alpha-level of 5% as the criterion for statistical significance. Outcome data missing, for whatever reason, will not be imputed.

For Aim 2. A two-tailed dependent T-test of the change in femoral neck BMD by DXA and failure load measured at the distal radius by HR-pQCT from pre-treatment to the 6-month endpoint will be reported with an alpha-level of 5% as the criterion for statistical significance. Secondary endpoints include treatment differences in change in cortical density, thickness and porosity, trabecular density and thickness and spacing, and areal BMD at the forearm, spine, and total hip. Other predictors to be tested in multiple regression models of change from baseline include demographic characteristics collected in **Aim 1** and PTH, calcitropic hormones, bone formation and resorption markers, sclerostin, and FGF-23 collected in **Aim 3**. A final multiple regression model will be based on predictors that are significant in multiple regression models including baseline bone measure.

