 1. Decreasing the dose of etelcalcetide can be implemented after the above steps have been undertaken. The dose should be lowered in 2.5 mg increments and monitoring of PTH and calcium should be obtained within a week of any changes.
 - d) Drop in serum calcium < 7.5 mg/dL or below the reference range with symptoms of hypocalcemia
 - i) Hold drug and monitor as per HD unit safety protocol
 - (1) If repeat calcium level WNL: restart dose at 2.5-5.0 mg lower than the previous dose and monitor as per HD unit safety protocol
 - (a) If repeat calcium level remains WNL and PTH at goal: no dose change
 - (b) If repeat calcium level remains WNL and PTH above goal: increase dose by 2.5 mg and monitor per HD unit safety protocol
 - (i) If calcium level < LLN but ≥ 7.5 mg/d without symptoms: follow algorithm 4c
 - (ii) If calcium level < 7.5 mg/dL or below the reference range with symptoms of hypocalcemia: proceed as per 4di
 - 5) Management of excessive suppression of PTH below the KDIGO target (< 2x LLN)

- i) Measure PTH after 4 weeks from initiation or dose adjustment
- ii) Without hypocalcemia: decrease dose by 2.5-5.0 mg and monitor as per HD unit safety protocol
- iii) With hypocalcemia: as per (4) above

Sample Size for Aim 1. N = 20

Sample Size Justification for Aim 1. The proposed sample size of 20 participants provides 80% power and 5% alpha for a two-tailed dependent T-test of the within-subject difference in the pre- and post-treatment hardness measured by Ramen/nanoindentation in the formation regions of 0.91-SDs. While we expect moderate variability in hardness between subjects, the within subject change due to treatment sought here is expected to be relatively similar across subjects given the established efficacy of etelcalcetide on other outcomes¹³. Behets et al¹⁴ reports patients with end stage renal disease show a baseline bone formation rate of 799 ± 334 (mean \pm SD), a O.Pm/B.Pm(%) of 18.9 ± 9.4 and a E.Pm/B.Pm of 13.1 ± 4.3 which assures a measurable region for the Ramen/nanoindentation assessment of hardness.

Sample Size for Aim 2. N = 35 (20 from Aim 1 plus 15 additional patients)

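### The Aim 1 assurance of a measurable region rests on untreated values only, and no rule covers a biopsy without a post-treatment double label

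*Combined protocol and SAP*

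**What the plan says.** All places are in the combined protocol and SAP.

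- **Sample Size Justification for Aim 1.** Patients with end-stage renal disease in a cited study "show a baseline bone formation rate of 799" (SD 334), with an osteoid perimeter of 18.9 ± 9.4% and an eroded perimeter of 13.1 ± 4.3, "which assures a measurable region for the Ramen/nanoindentation assessment of hardness". No on-treatment value is quoted, although the reference list titles the source as a before-and-after study of another calcimimetic.
- **Hypotheses (opening page).** The expectation is that "etelcalcetide treatment improves bone tissue-properties and bone mineral density by reducing remodeling".
- **Aim 1, Procedures.** Tetracycline labels are given before the drug. Demeclocycline labels are given after 3 months of titration and 6 months of maintenance. One biopsy at the end supplies both time points.
- **Bone-tissue properties.** "Areas within the TCN and demeclocycline double label will be assessed for nanoindentation properties", and "A total of 12-15 indentations will be performed within a given region".
- **Primary and Secondary Endpoints.** Hardness is primary for Aim 1. Bone formation rate is secondary.
- **Statistical methods, For Aim 1.** The analysis is a paired t-test. "Outcome data missing, for whatever reason, will not be imputed".

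The documents contain no rule for an absent, single or too-small label, no minimum label area, and no allowance for non-evaluable biopsies.

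**The concern.** The evidence and the claim concern different time points. Formation before treatment supports the presence of a tetracycline region. It does not show that a demeclocycline region will form after about nine months on a drug meant to slow remodeling. Eroded perimeter measures resorption, so it is not evidence of label at either time.

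This matters because an absent post-treatment label is not an ordinary missing value. In a readable biopsy from a patient who took the label drug, it is a finding of little or no formation. If that patient has no calculable formation rate and is not imputed, the paired test loses one of the lowest post-treatment values and the mean fall shrinks. For hardness, the patient has no post-treatment region to indent. The result then describes patients with both labels readable, whereas Hypothesis 1 is framed for patients with ESKD and severe hyperparathyroidism in general.

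**Working it through.** **1. The plan's own figure.** The plan says that "The proposed sample size of 20 participants" "provides 80% power and 5% alpha for a two-tailed dependent T-test" at 0.91 SD. For a paired t-test with n = 20, df = 19 and noncentrality 0.91 × √20 = 4.07, power is 97.1%, not 80%. The difference detectable with 80% power is 0.66 SD. The value 0.91 is what an independent two-sample t-test with 20 per group detects (80.1% power). The plan does not say which SD it means; with single-time SDs and zero pre/post correlation, the paired test gives 77.9%. This mismatch is a separate matter. What counts here is that the calculation treats all 20 pairs as evaluable.

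**2. What the baseline values show.** Mean minus 2 SD is 799 − 2 × 334 = 131 for formation rate and 18.9 − 2 × 9.4 = 0.1% for osteoid perimeter. No distribution is assumed. The spread is wide before any suppression, so even at baseline these figures do not assure a region in every patient.

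**3. Bone formation rate (illustration).** Only 799 comes from the plan. Assume that labelled patients fall to 400, that k of 20 have no demeclocycline label with true formation 0, and that those k are dropped.

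- Reported fall = 799 − 400 = 399, whatever k is.
- True post-treatment mean = 400 × (20 − k)/20.

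| k | True post mean | True fall | Reported fall | Understated by |
|---|---|---|---|---|
| 2 | 360 | 439 | 399 | 40/439 = 9% |
| 3 | 340 | 459 | 399 | 60/459 = 13% |
| 5 | 300 | 499 | 399 | 100/499 = 20% |

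**4. Hardness (illustration).** Assume a true change of 0.91 SD of the differences.

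- Random loss of 4, 6 or 8 pairs leaves power of 92.5%, 88.2% or 81.8%. Lost numbers alone are tolerable at that effect size.
- Suppose the 4 patients with the largest fall in formation are lost, and that fall correlates 0.3, 0.5 or 0.7 with the hardness change. In simulation the observed mean drops to 0.81, 0.74 or 0.68 SD, with power of 87%, 82% or 79%.
- Suppose instead that the 4 patients with the smallest fall are lost, for example because continued remodeling removed their tetracycline label. By symmetry the shifts of 0.10, 0.17 and 0.23 go the other way, giving 1.01, 1.08 or 1.14 SD.

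The documents give neither the correlation nor which loss would dominate, so the sign of any net hardness bias cannot be derived.

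**The case against.** The plan has real safeguards. Aim 1 requires PTH above 9 times the ULN on two consecutive monthly checks and total alkaline phosphatase in the upper tertile or above. PTH is then to be held at 300-400 pg/mL. With the ULN implied by the inclusion criteria (720/9 = 80), that is 3.75 to 5 times the ULN, inside the 2-9 range the plan cites. A separate item addresses excessive PTH suppression. The plan therefore aims at moderated turnover, not absent formation. The alkaline phosphatase criterion acts only before treatment, however, and the over-suppression item shows that the plan allows for overshoot. The safeguards lower the risk without removing it.

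The analysis section does not itself class an unlabelled biopsy as missing, and the histomorphometry section defers definitions to a professional standard that is not reproduced. So such a patient *can* drop out; it is not certain that the patient will. That gap is a reason to write the rule down. It is also fair that the sample size text already places hardness in formation regions, so part of the limit on scope is implicit.

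A reader might infer three stronger points that the documents do not support:

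- **That the most suppressed patients will be removed and hardness biased toward no effect.** No frequency of absent label is given. Loss of tetracycline label in poorly suppressed patients could act in the opposite direction.
- **That the labelled band would be no wider than the indent.** At an assumed hardness of 0.3-0.7 GPa, a 10 mN indent is 5.7-8.8 µm on a side. At an assumed 0.3-0.5 µm/day over 15 days between label midpoints, the band is 4.5-7.5 µm. A 7.5 µm band exceeds a 5.7 µm side, so the statement fails within its own range, and neither input is in the documents.
- **That absent label always means zero formation.** The bone biopsy risk section tells subjects to stop the label drug if gastrointestinal symptoms develop, so absent label can mean that it was not taken.

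**Conclusion.** The point holds as a gap in evidence and in analysis rules. The assurance is not supported by what is cited for it, because every value is pre-treatment and the critical region forms on treatment. With no imputation and no label rule, the fall in bone formation rate can be understated. The 9% to 20% shown is conditional on the assumed 400, the assumed zeros and 2 to 5 unlabelled patients of 20; it is not a prediction. The hardness result applies only to patients with both labels readable, and the direction of any bias there is unknown. Reading reduced remodeling as reduced formation is itself an inference, since the plan states no expected direction for formation rate. On-treatment values in the cited source might prove reassuring, but the plan does not quote them. This should be corrected before the labels are read, since a rule chosen afterwards would be data-driven.

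**What to change.** 1. **Sample Size Justification for Aim 1.** Replace *assures* with a statement that the supporting evidence is baseline only, or cite on-treatment formation or label values.
2. **Statistical methods, For Aim 1.** Add a rule for readable biopsies:
   - With documented demeclocycline intake and no demeclocycline label, count bone formation rate and activation frequency as 0.
   - With documented intake and single label only, use a minimum apposition rate fixed in advance.
   - With absent label and no documented intake, treat the value as missing.
   - Report results with and without the patients to whom the zero or minimum rule applies.
3. **Reporting.** State how many of the 20 have evaluable tetracycline and demeclocycline regions, with their PTH and BSAP, and limit the hardness conclusion to those patients.

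Indenting single-label regions is not a useful remedy. At an assumed 0.3-1.0 µm/day, a 3-day label is 0.9-3.0 µm wide, against an indent side of 5.7-8.8 µm under the hardness assumption above.

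The cost is a few sentences, a record of label intake and one sensitivity analysis on the same biopsies. The drawback is that the minimum apposition rate is a convention.

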Procedures. We will enroll 35 patients (20 from Aim 1 and 15 *de novo*) into this prospective single-arm cohort study to test the hypothesis that 6 months of treatment (maintenance) with etelcalcetide will improve bone density, microarchitecture and mechanical competence measured by DXA and HR-pQCT with application of finite element analysis (FEA). Similar to **Aim 1**, eligibility for enrollment into **Aim 2** will be based on a PTH level >9 -times the ULN for the PTH assay (**Figure 1**), as well as their treating physician's plan to initiate etelcalcetide per standard of care. However, the presence of high turnover bone disease based on total alkaline phosphatase will not be a criterion for enrollment into **Aim 2**. Furthermore, all patients enrolled in **Aim 1** will be automatically enrolled into **Aim 2** unless they choose to opt-out of **Aim 2**. As per **Aim 1** (**Figure 2**), after enrollment, patients will undergo a 3-month dose titration phase to ensure that PTH levels are stability maintained within the target range (300-400 pg/mL), followed by a 6-month treatment (maintenance) phase. All patients will have imaging (DXA and HR-pQCT) performed at baseline (prior to drug) and after 6-months of maintenance treatment.

Imaging Methods for Measurement of Bone Mass, Microarchitecture, and Mechanical Competence

- **DXA.** areal BMD of spine (L1-4, AP), right proximal femur, forearm and whole body using Hologic QDR 4500 (Hologic, Inc., Waltham, MA) in the array (fan beam) mode. Phantoms are scanned daily for QA. Short term, *in vivo* precision is 0.68%, 1.36%, and 0.70% for spine, FN, and radius respectively.
- **HR-pQCT of the ultradistal radius and tibia.** XtremeCT2 (Scanco Medical AG, Brüttisellen, Switzerland, voxel size 60 μ m). Methods and QC are described in our publications^{6, 7}. Precision: cortical and volumetric trabecular BMD=0.9% \pm 7.1% and 2.3 \pm 3.5%, respectively. HR-pQCT of the forearm will be performed at the non-dominant forearm. If dialysis access is located at the non-dominant forearm, we will use the dominant forearm for HR-pQCT imaging.

Mechanical Analysis of Skeletal Imaging. [name] MS will perform analyses of HR-pQCT datasets.

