Sample Size Justification for Aim 2. The proposed sample size of 35 participants provides >80% power and 5% alpha to detect a change in femoral neck BMD of 0.5% f and a 0.5 standard deviation change in radius failure load by HR-pQCT from pre-treatment to the 6-month endpoint. For femoral neck BMD by measured by DXA, Lien et al¹⁵ reported that in 8 patients with CKD treated with cinacalcet for 6 months, areal BMD at the femoral neck increased $2.2 \pm 1.1\%$ ($p < 0.05$). For failure load outcomes, in a longitudinal study of 29 patients with ESKD who underwent kidney transplantation, we reported that failure load decreased by $3.5 \pm 7.0\%$ ($p=0.0081$) over 12-months¹⁶; our larger sample size will permit detection of at least a 3.4% change in radius failure load due to suppression of PTH production by etelcalcetide.

Sample Size for Aim 3: N = 35 (20 from Aim 1 plus 15 additional patients)

Sample Size Justification for Aim 3: The proposed sample size of 35 participants provides >80% power and 5% alpha two-tailed dependent T-test of the change in T50 from baseline to the 6-month endpoint. Based on Smith et al¹⁰, each standard deviation (SD) decrease in T50 was associated with a 39% increase in odds of all-cause mortality. Assuming that the variability in T50 in patients on hemodialysis patients enrolled into this prospective cohort study are similar to those reported in Smith et al¹⁰, approximately 20 patients would be required to detect a 1-SD decrease in T50. Our sample size of 35 patients will permit the detection of a 0.7-SDs decline in T50. We assume that a reduction of lesser magnitude is of unclear clinical significance

Protection of Human Subjects

This study qualifies as clinical research and will be conducted in compliance with GCP and all regulatory requirements for the protection of human subjects.

Informed Consent

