- **Hypocalcemia.** Etelcalcetide has been associated with a decrease in serum calcium. We will monitor for and minimize this risk as described in the main protocol.
- **Loss of confidentiality.** due to breaches in data security or deductive disclosure. To ensure that participants' confidentiality is not compromised, we will minimize these risks through the procedures discussed below.
- **Radiation.** The total expected radiation dose for the entire study is approximately 8 mrem (80 μ Sv) for 2-sets of DXA and HR-pQCT scans obtained at the baseline and 12-month visits. This compares to 2400 μ Sv natural background in a year, 8000 μ Sv for a standard chest CT, 450 μ Sv for a mammogram, and 60 μ Sv for a round-trip transcontinental plane flight. The total radiation exposure for the study will be below the maximal acceptable dose.
 - a) **CUMC DXA (2 sets of scans).** Radiation exposure for DXA (spine, one hip, forearm) using the Hologic QDR4500 (fast scan) is 10.85 μ Sv (21.68 μ Sv for 2 sets of scans).
 - b) **HR-pQCT (one forearm and one leg; 3 sites each).** 30 μ Sv (60 μ Sv for 2 sets of scans)
- **Transiliac crest bone biopsy.** The risks of the bone biopsy include those related to tetracycline and demeclocycline administered in advance of the biopsy to label sites of bone formation, the risks of conscious sedation, and the risks of the biopsy itself. Tetracycline-type agents may cause stomach upset and skin rashes when subjects taking them are exposed to sunlight. Subjects will be counseled to discontinue tetracycline/demeclocycline if gastrointestinal symptoms develop and to avoid sunlight exposure during the 6 days they are taking the medication. Conscious sedation will be offered to subjects in order to minimize anxiety, provide pain relief, and diminish recall. Patients receiving conscious sedation may have brief, transient loss of protective reflexes. Either IV or PO sedation will be provided with a combination of a benzodiazepine (e.g, midazolam, valium) and a narcotic-based pain medication (e.g., fentanyl, oxycodone). Risks will be minimized by complying with all procedures as required by CUMC's Policies and Procedures Manual. Specifically, all nurses and physicians involved in performing bone biopsies will have certification in Advanced Cardiac Life Support, the procedure will be conducted in the Biopsy Suite in the Division of

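### Aim 2 sample size: 35 patients give 74%, not more than 80%, power for a 0.5% femoral neck BMD change at the cited SD of 1.1%, and that SD is not reconciled with the protocol's own 1.36% DXA precision

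*Combined protocol and SAP*

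**What the plan says.** Femoral neck BMD change is one of the two primary endpoints of Aim 2; radius failure load is the other. The Sample Size Justification for Aim 2 says that the planned enrolment "provides >80% power and 5% alpha to detect a change in femoral neck BMD of 0.5% f and a 0.5 standard deviation change"; the second of these changes refers to failure load. It names no planning SD for the femoral neck. The only support is a cited study in which "in 8 patients with CKD treated with cinacalcet for 6 months, areal BMD at the femoral neck increased" by 2.2 ± 1.1%, with p<0.05. For failure load, it cites a 12-month change of 3.5 ± 7.0% in 29 transplant patients and adds that "our larger sample size will permit detection of at least a 3.4% change in radius failure load".

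Three other places bear on the claim:

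- Statistical methods, For Aim 2, fixes the test: "A two-tailed dependent T-test of the change in femoral neck BMD by DXA", at 5% alpha.
- The DXA item under Imaging Methods states that short-term in vivo "precision is 0.68%, 1.36%, and 0.70% for spine, FN, and radius respectively".
- The Radiation item under Potential Risks counts "2-sets of DXA and HR-pQCT scans obtained at the baseline" and one later visit over the whole study, so there is one DXA set per visit.

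**The concern.** A power statement needs a sample size, a test, an effect and an SD. The first three are given. The only candidate for the fourth, 1.1%, does not produce the stated power at the stated effect. It is also smaller than the protocol's own precision figure for the same measurement. A change score contains the measurement error of two scans, so its SD would normally exceed the error of one scan, even if every patient responded identically.

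At stake is how the femoral neck result will be read. If it is null, readers will use the printed 0.5% to judge how small an effect the study could have seen. If the real sensitivity is nearer 0.9%, a null result excludes much less than the plan implies.

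**Working it through.** **Inputs.** n = 35 (Sample Size for Aim 2); two-tailed paired t-test at 5% (Statistical methods); effect 0.5%; femoral neck spread 1.1% from 8 patients; failure-load spread 7.0%; femoral neck precision 1.36% (Imaging Methods, DXA).

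**Formula.** d = change / SD of change. Power comes from the noncentral t distribution with 34 df and noncentrality d × √35. Solving for 80% power at n = 35 gives d = 0.4875.

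**Reproducing the plan's failure-load figures.** 0.4875 × 7.0% = 3.41%, which matches the stated 3.4%. A change of 0.5 SD has 82.0% power, which matches the claim of more than 80%. The plan therefore appears to have used this two-sided rule.

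**The same rule for the femoral neck.**

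- d = 0.5 / 1.1 = 0.4545; noncentrality 0.4545 × 5.916 = 2.69; power 74.3% (normal approximation 76.7%).
- Detectable change at 80% power: 0.4875 × 1.1% = 0.536%.
- To have 80% power at exactly 0.5%, the SD must be no more than 0.5 / 0.4875 = 1.026%, or n must be 40 at SD 1.1%. The documents give no SD that small.

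**Is 1.1% an SD or an SE?** With n = 8:

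- As an SD: t = 2.2 / (1.1/√8) = 5.66, p = 0.0008, consistent with the quoted p<0.05.
- As an SE: t = 2.2 / 1.1 = 2.0, two-sided p = 0.086, not consistent. The SD would then be 1.1 × √8 = 3.11% and power 15%, which is worse for the plan.

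**Floor on the SD of change from measurement error.** The plan does not define the 1.36%, so two assumptions are shown. Both take short-term precision as applying to these patients.

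- A: one-SD error per scan, independent between the two visits. Floor = √2 × 1.36% = 1.92%.
- B: already the SD of a difference between two scans. Floor = 1.36%.

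| SD of change | Source | Power at 0.5% | Detectable at 80% power | Power at 2.2% |
|---|---|---|---|---|
| 1.1% | cited study | 74% | 0.54% | >99.9% |
| 1.36% | assumption B, lower bound | at most 56% | at least 0.66% | >99.9% |
| 1.92% | assumption A, lower bound | at most 32% | at least 0.94% | >99.9% |

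The last column takes each listed SD as the actual SD. All rows are before any multiplicity adjustment within the DXA domain.

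**How firm is 1.1%?** The 95% interval for an SD of 1.1 on 7 df runs from √(7 × 1.21 / 16.01) = 0.73% to √(7 × 1.21 / 1.69) = 2.24%. It contains both floors.

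**The case against.** The strongest reply is that 0.5% is just 0.536% printed to one decimal, as other percentages in that paragraph are. The method is sound, as the 3.4% shows, and a headline of 74% makes a rounding choice look like a failed calculation. This largely stands as an explanation of the first discrepancy. It does not make the sentence right: at 0.5% power is below 80%, and rounding a detectable change downward overstates sensitivity.

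Second, the sentence is garbled after 0.5%, perhaps only in the PDF reading, and 0.5 SD may have been meant. That reading does give 82% power. But 0.5 SD is 0.55% at SD 1.1%, 0.68% at 1.36% and 0.96% at 1.92%, so the printed percentage is still too small.

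Third, the 1.1% is not labelled as an SD or as the planning value. True; both are inferences. A one-sided test on the SE reading would give p = 0.043, so that reading cannot be wholly excluded. It would lower the power further.

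Fourth, the precision argument rests on an undefined figure, and the interval for the 8-patient SD covers 1.36% and 1.92%, so the two sources do not formally conflict. This is fair, and no true SD of change is known. But it means that the 8-patient SD cannot be used to set aside the protocol's own precision figure. Both readings of that figure point the same way.

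Finally, nothing in the trial's conduct changes. That stands, and it limits the severity.

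**Conclusion.** The concern holds. As written, the claim of more than 80% power for a 0.5% femoral neck change is not supported by any SD in the documents. Taking the cited 1.1% as the SD of change, power is 74% and the detectable change 0.54%. This is a minor discrepancy, probably due to rounding.

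The more important part is conditional on what 1.36% means. If it is an independent per-scan error, the detectable change is at least 0.94%, nearly twice the printed value. If it is the SD of a difference, it is at least 0.66%. Both remain optimistic because they leave out real differences in response between patients.

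Only the stated sensitivity for this primary endpoint fails. Power at the 2.2% effect that the plan cites stays above 99.9% at all three SDs, and the failure-load statement reproduces. The plan also does not say whether the 5% in the power statement is before or after the step-down adjustment within DXA. That is a missing detail, and the conclusion does not depend on it.

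**What to change.** Revise the Sample Size Justification for Aim 2:

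1. State the SD of femoral neck change used and its source.
2. Say whether the 1.36% is a per-scan error or the SD of a difference, and reconcile it with the 1.1%.
3. Replace 0.5% with the 80%-power detectable change that follows: about 0.94% on the per-scan reading, about 0.66% if 1.36% is the SD of a difference, or 0.54% only if an SD of 1.1% is justified. On the first two readings, call the figure a lower bound.
4. Repair the garbled text after 0.5%.
5. Add a clause saying whether the 5% alpha is before or after the within-DXA adjustment.

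The cost is wording in one paragraph, with no extra patients and no change to design or analysis. The downside is a less favourable stated sensitivity.
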